##### **Secondary endpoints**

Sensitivity of targeted-only samples for each modality will also be calculated in order to determine the effectiveness of a targeted only biopsy technique in each case. Presence of cancer per-target will also be assessed, along with detailed pathological findings, and targeting modality identifying the lesion. Size and shape of lesions will also be recorded from recorded images.

### **5.8.1.4 Variables**

The sensitivity, specificity and area under the ROC curve for accurate identification of clinically significant prostate cancer for each modality will be determined, along with the corresponding credible intervals. Summary statistics will be provided for all modalities.

Biopsy results may fall into 4 categories based on pathology review:

1. Clinically significant cancer (GS > 6)
2. Clinically insignificant cancer (GS = 6)
3. Cancer precursors (HGPIN, Atypia)
4. Benign (including findings of Prostatitis)

Distribution of findings for all categories, and comparison of these distributions between modalities will also be reported.

### **5.8.1.5 Assessing variables**

The analysis to be performed on data collected during the investigation will be done on software customized and validated by Exact Imaging. This software will be maintained as per Exact Imaging's internal operating procedures. The software will not be 'calibrated' other than if there are instances where the software does not perform as required against unusual or exceptional data.

A third-party statistician will be contracted to independently confirm all results.

### **5.8.1.6 Replacing subjects**

Case data for all enrolled study subjects will be included in the analyses. Because a subject's involvement ends following his biopsy procedure, and because it is not expected that a subject will drop-out after his biopsy procedure, the need to replace subjects is expected to be unlikely.

If a subject needs to be replaced, he will be consented as per processes described for all study subjects.

## **5.8.2 Medical devices and comparators**

The ExactVu micro-ultrasound system with high-frequency EV29L transducer will be used. The FusionVu software package will be used for software assistance during mpMRI-US fusion. This device, including all software and hardware components are cleared by FDA for the prostate biopsy and mpMRI fusion biopsy procedure in the United States.

## **5.8.3 Subjects**

### **5.8.3.1 Inclusion criteria for subject selection**

Subjects will be recruited to participate in the investigation as follows:

1. Men presenting for prostate biopsy due to clinical suspicion of prostate cancer
2. 40-75 years old
3. Available mpMRI images and report, performed according to the PI-RADS v2 standard

Patients who choose not to participate will be offered a standard of care prostate biopsy. No patient will be denied appropriate medical care based on their willingness to participate in this trial.

### **5.8.3.2 Exclusion criteria for subject selection**

Subjects will be excluded from being included in the investigation if any of the following is true:

1. Men with anorectal abnormalities preventing TRUS-guided prostate biopsy
2. Men who are unable to provide their own informed consent
3. Prostate volume on MRI > 100cc

### **5.8.3.3 Criteria and procedures for subject withdrawal or discontinuation**

Subjects may withdraw from the investigation at any time with no effect on their future care.

If a subject wishes to stop participating in the investigation, they are to do so by notifying the Principal Investigator by phone or letter.

If a subject withdraws from the investigation prior to having his biopsy procedure performed, the biopsy procedure will be performed as per the normal standard of care. There will be no further follow-up with this subject in the context of this investigation.

Data considerations for this case are provided in section 5.9.

### **5.8.3.4 Point of enrolment**

Men meeting the criteria defined in section 5.8.3.1 will be asked to participate in the study and will be presented with a *Research Subject Information and Consent Form*.

Subjects are considered to be enrolled in the investigation when they return a signed Research Subject Information and Consent Form to the Principal Investigator.

When a signed form is presented, the subject agrees to join the investigation, and accepts the provisions on the form, including an understanding that he may leave the investigation at any time.

NOTE: Informed consent documentation will be provided in English for potential subjects.

### **5.8.3.5 Total expected duration of the clinical investigation**

The investigation is expected to take approximately 12 months maximum.

### **5.8.3.6 Expected duration of each subject's participation**

The procedure follows the standard of care, in that a prostate biopsy is performed. Subjects are not required to come for additional clinic visits in the context of the investigation.

Participating in the trial will add approximately 5-10 minutes to the subject's procedure time.

### **5.8.3.7 Number of subjects**

The number of subjects to be included in the trial is 120.

### **5.8.3.8 Estimated time needed to select this number (i.e. enrolment period)**

The investigation is expected to take approximately 12 months in total. This is intended to provide Urology San Antonio with adequate time to enroll and study the projected number of subjects in the trial. A subject's participation in the investigation is completed following his prostate biopsy.

## **5.8.4 Procedures**

### **5.8.4.1 Clinical investigation-related procedures**

The procedures affecting subjects and investigators participating in the investigation are:

- Consent / Subject Enrolment as described in section 5.15
- Training as described in section 5.4.5
- Medical procedure as described in section 5.4.6
- Record Data on Case Report Forms as described in section 5.8.6
- Analyze Data as described in section 5.9

### **5.8.4.2 Sponsor activities**

Exact Imaging's responsibilities as the sponsor of this clinical investigation include the preparation of this CIP. These responsibilities are presented in detail, to facilitate planning of this investigation.

Exact Imaging will supply Urology San Antonio with:

- Sterile needle guides and transducer sheaths required for biopsy procedures to be performed on the ExactVu system
- Exact Imaging will not provide biopsy needles, a biopsy gun (if used), surgical gloves or gel, an ExactVu system, or EV29L transducer

Exact Imaging will fund the study, with an approved budget that is incorporated into the Clinical Trial Agreement.

Further detailed sponsor responsibilities can be found in Appendix A.

### **5.8.4.3 Compromising factors**

There are no known foreseeable subject-related factors such as subject baseline characteristics and lifestyle that may compromise outcomes or the interpretation of results.

### **5.8.4.4 Follow-up period**

Following a subject's biopsy procedure, there is no further follow-up involved in the context of this investigation.

### **5.8.4.5 Post-investigation care**

No further medical care is provided within the context of this investigation.

If a pathology report indicates that further treatment is required, this will take place as per standard of care, but this is outside the scope of this investigation, and no data pertaining to further treatment will be used in the analysis for this investigation.

## **5.8.5 Monitoring Plan**

Exact Imaging will assign personnel to the Study Monitor role for the investigation, and agrees to adhere to the monitoring responsibilities, which include verifying that:

- a) compliance with the CIP is maintained and any deviation from the CIP is discussed with the clinical investigators, documented and reported to the sponsor,

- b) the device is being used according to the CIP, and if modifications are required either to the device or its method of use or to the CIP, this need is reported to the sponsor,
- c) the clinical investigators have and continues to have staff and facilities to conduct the clinical investigation safely and effectively,
- d) the clinical investigators have and continues to have access to an adequate number of subjects and devices,
- e) signed and dated informed consent forms have been obtained from each subject at the time of enrolment and before any study-related procedures are undertaken,
- f) the data in the case report forms are complete, are recorded in a timely manner and are consistent with the source data, the procedures for recording and reporting adverse events and adverse device effects to the sponsor are followed,
- g) there is a process in place for device accountability and traceability and that it is maintained,
- h) maintenance and calibration of the equipment relevant for the assessment of the clinical investigation is performed and documented,
- i) subject withdrawal and/or non-compliance is documented and discussed with the clinical investigator and reported to the sponsor,
- j) findings of non-compliance or required modifications shall be reviewed with the investigator and disclosed in a written monitoring report to the sponsor.

Source data will be recorded on case report forms (CRFs) as described in section 5.8.6.

### **5.8.5.1 Site Visits**

Further to the description of Exact Imaging's role as the Study Monitor for the investigation, Exact Imaging will ensure the quality of data related to the investigation by:

- on-site visits to Urology San Antonio at the beginning and end of the study
- thorough review of CRF data to identify and follow-up on missing data, inconsistent data, data outliers, and potential CIP deviations that may be indicative of systemic or significant errors in data collection and reporting
- 100% verification of all data

An on-site visit at the beginning of the investigation will include the following activities:

1. Review of supplies required for the investigation
  - a. Check that there continues to be an adequate supply of sterile transducer sheaths and needle guides

An on-site visit at the beginning of the investigation will include the following activities:

1. Review issues with investigators
  - a. Study Monitor will discuss and investigate any performance issues and device deficiencies and resolved as required. These issues will be documented and signed by the Study Monitor, including details about steps taken to resolve issues
  - b. Review any changes to the investigative team and update details in the CIP as required
  - c. Provide training where changes to the investigative team requires it
2. Review subject enrolment
3. Review study data
  - a. Review data collected on CRF
  - b. Check CRF for completeness and accuracy. Ensure CRFs are filled out properly
  - c. Check ExactVu for images. There must be one image saved on the system to correspond to each biopsy core.

- d. Verify data. Compare images stored on ultrasound system with CRF data and pathology report
4. Copy and collect image data
5. Copy and collect completed CRFs

Along with providing assurance of the quality of investigational data, these actions will allow Exact Imaging to assess compliance with the CIP and required procedures.

For cases in which the Study Monitor observes biopsy procedures during a site visit, the Study Monitor shall neither perform medical procedures nor contact the study subject, but will provide support through instruction where required.

### **5.8.6 Case Report Forms**

The case report form to be used in this investigation is designed to collect information about the location of the prostate where biopsy samples were taken, to provide a summary of findings from the pathology report entered locally, along with other notes from investigators.

Source data will be recorded on case report forms (CRFs) as follows:

- For each of the 12 systematic biopsy samples, investigators will indicate the PRI-MUS score for micro-US. (For every biopsy sample, an image of the biopsy location will be saved on ExactVu as well.)
- For each additional targeted biopsy sample, investigator will indicate the location and the PRI-MUS score for micro-US. (For every biopsy sample, an image of the biopsy location will be saved on ExactVu.)
- Pathology report will be entered on the CRF and a copy attached to the CRF. This is checked for accuracy by the Principal Investigator.
- mpMRI report will be entered on the CRF and a copy attached to the CRF. This is checked for accuracy by the Principal Investigator.

Note that the PRI-MUS protocol used here is derived from Ghai et al.. This protocol for assessing risk in the micro-US images is investigational and has not been evaluated by the FDA.

Along with the data accuracy checks listed above, Exact Imaging will also check data prior to and during analysis as follows:

- Check pathology reports against what is entered on the CRF
- Logic checks on data, and follow-up on unusual data. (For example, if there is a case in which biopsy samples from targeted needles don't indicate cancer and samples from systematic needles do show cancer, an investigation would follow.)

Analysis of data is described in the subsections of section 5.9.

The case report form to be used in this investigation is controlled as per Exact Imaging's standard operating procedures.

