#### **5.9.11 Exclusion of data**

Conditions that would result in the exclusion of data would be if any data verification activity showed that data was recorded on the CRF incorrectly, or if the pathology report showed any inconsistency with information on the CRF.

If such incorrect data was discovered, data for this subject will not be included in any analysis, and the CRF for the subject will be marked to indicate that the data is excluded.

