### **5.10.2 Data verification and validation**

Source data will be recorded on case report forms (CRFs) as described in section 5.8.6.

Source data will be verified during on-site visits by the Study Monitor, as described in section 5.8.5.1.

This data will be collected by the Study Coordinator or Study Monitor, and forwarded to Exact Imaging personnel for analysis. The accuracy of the data will be verified by Exact Imaging by manual comparisons between:

- data on CRFs and pathology reports
- data on CRFs and on images stored on ExactVu
- images stored on ExactVu and data on pathology reports

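### Section 5.8.6 names one result pattern (targeted cores negative, systematic cores positive) as its only example of unusual data; with the exclusion rule in 5.9.11 this risks outcome-dependent exclusion

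*Combined protocol and SAP*

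**What the plan says.** Section 5.8.6 (Case Report Forms) describes sponsor checks on top of those done at the site: "Exact Imaging will also check data prior to and during analysis as follows". One item is a general rule on logic checks and odd-looking records, which the section illustrates with a subject whose "biopsy samples from targeted needles don't indicate cancer and samples from systematic needles do show cancer, an investigation would follow". No other example is given, and the reverse pattern (targeted positive, systematic negative) is not mentioned.

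Routine verification does not depend on results. Section 5.8.5.1 promises "100% verification of all data", and 5.10.2 adds: "The accuracy of the data will be verified by Exact Imaging by manual comparisons between" CRFs, pathology reports and stored images.

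Section 5.9.11 states the consequence of a finding. Data are excluded if any verification activity shows a wrong CRF entry, or "if the pathology report showed any inconsistency with information on the CRF". The whole subject then leaves every analysis. Section 5.9.10 likewise treats incorrect records as not used. Neither section describes correcting the entry and keeping the subject.

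**The concern.** Systematic cores are taken because targeting can miss. A subject whose targets are negative and whose systematic cores are positive is therefore an expected result and no sign of a recording error. If the sponsor looks harder at such subjects, with pathology already known, it will find more CRF errors among them than among equally error-prone subjects with other results. Under 5.9.11 each error found costs the subject his place in the analysis, so exclusion would depend partly on the outcome being measured.

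The targeted-only comparison is exposed. It is the primary outcome in 5.7.1, 5.7.2 and 5.9.5, and a secondary endpoint in 5.8.1.3 ("Sensitivity of targeted-only samples for each modality will also be calculated"). The trial passes or fails on the ratio of micro-ultrasound to mpMRI sensitivity, whose lower one-sided 95% bound must not fall below 0.76.

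**Working it through.** **1. What the trigger catches.**
- Under the targeted-only outcome (5.7.1, 5.7.2, 5.9.5), negative targets with csPCa in systematic cores are a miss.
- Under the primary endpoint text of 5.8.1.3 (systematic plus that modality's targets), the same subject counts as detected by both modalities.
- The trigger is any cancer, whereas the endpoint is csPCa (ISUP 2 or higher). It therefore flags systematic Gleason 6 findings that are not misses, and passes over a target with Gleason 6 alongside systematic csPCa, which is a miss.
- The text names no modality. It may apply to each modality's targets separately or to both together.

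**2. Notation.** Among csPCa subjects: a = detected by both, b = micro-ultrasound only, c = mpMRI only, d = neither.
- Ratio R = (a+b)/(a+c).
- SE of ln R = √[(b+c)/((a+b)(a+c))].
- Pass if exp(ln R − 1.645·SE) ≥ 0.76.

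**3. At the plan's own assumptions.** Sections 5.9.1 to 5.9.3 give 120 subjects, 60% prevalence (120 × 0.60 = 72 csPCa), sensitivities 0.85 and 0.90, and 80% agreement. Then b+c = 0.20 and c−b = 0.05, so b = 0.075, c = 0.125, a = 0.775, d = 0.025. Times 72, the counts are a 55.8, b 5.4, c 9.0, d 1.8, and R = 61.2/64.8 = 0.944.

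| Subjects removed | Formula | Ratio |
|---|---|---|
| 1, 2, 3 missed by micro-ultrasound only | 61.2/(64.8−k) | 0.959, 0.975, 0.990 |
| 1, 2, 3 missed by mpMRI only | (61.2−k)/64.8 | 0.929, 0.914, 0.898 |
| all 1.8 missed by both | unchanged | 0.944 |
| 1, 5, 10 detected by both (endpoint of 5.8.1.3, same cells for illustration) | (61.2−k)/(64.8−k) | 0.944, 0.940, 0.934 |

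Removing the double misses raises the sensitivities to 61.2/70.2 = 0.872 and 64.8/70.2 = 0.923. For a single subject, then, the direction depends on which modality missed and on which endpoint applies.

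**4. At the margin, modality-by-modality reading.** Assumed: 72 csPCa subjects, sensitivities 0.684 and 0.90 (ratio 0.76), independence, targeted-only endpoint. Expected counts:
- a = 72 × 0.684 × 0.90 = 44.3
- b = 72 × 0.684 × 0.10 = 4.9
- c = 72 × 0.316 × 0.90 = 20.5
- d = 72 × 0.316 × 0.10 = 2.3

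Remove the same fraction f of b and of c. The ratio at expected counts is [44.32 + 4.92(1−f)]/[44.32 + 20.48(1−f)]. Pass rates are from simulation with the rule in step 2.

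| f | Expected removed from c and b | Ratio | Pass rate |
|---|---|---|---|
| 0 | 0 and 0 | 0.760 | 6.4% |
| 5% | 1.0 and 0.2 | 0.768 | 8.1% |
| 10% | 2.0 and 0.5 | 0.777 | 10.2% |
| 20% | 4.1 and 1.0 | 0.795 | 16.1% |

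The baseline exceeds 5% because the log-ratio bound is approximate at this size. The rise comes from c being about four times b: removal with no favouritism takes more micro-ultrasound misses than mpMRI misses. Here f is a fraction of all single-modality misses, whereas the check reaches only those with positive systematic cores. The documents give neither that share nor an error rate, so 5% to 20% is an assumed range.

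**5. At the margin, pooled reading.** Only subjects missed by both are flagged. The count d enters neither R nor its SE, so the ratio and the pass rate (6.4%) do not move. Dropping all 2.3 raises the sensitivities from 0.684 to 49.25/69.72 = 0.706 and from 0.900 to 64.8/69.72 = 0.929.

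**The case against.** The case for leaving the text alone has real substance.

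- The sentence is one illustration within general checks, on top of full verification. A reader might infer that verification as a whole depends on the outcome; only the added investigation does.
- An investigation may confirm the data. A correctly recorded miss meets neither exclusion condition in 5.9.11. The inference that the check can only remove misses or turn them into hits is therefore not supported.
- A reader might also suspect one-sided relabelling, because every systematic core is taken by the micro-ultrasound operator and is scored: "For each of the 12 systematic biopsy samples, investigators will indicate the PRI-MUS score for micro-US". No section permits changing a core's origin after pathology. Section 5.4.6 has suspicious regions recorded before sampling and each targeted lesion put in its own labelled jar, and 5.8.6 requires an image per core. Under the step 4 assumptions, relabelling 2, 3 or 4 micro-ultrasound-only misses as hits would give pass rates of 15%, 22% or 30%, and dropping only those misses 13%, 17% or 23%. Both calculations assume selective handling that the documents do not describe.
- On the pooled reading, which is arguably the plainer one, the ratio is not touched at all.
- An independent statistician analyses the data (5.9.1). This protects less than it seems to, because sponsor staff verify the records and transfer them to the analysis tool (5.10, 5.10.2), so an exclusion would occur before the statistician sees the data.

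These points limit the claim but leave its core intact: the only named trigger is a valid result, it has no mirror, and the stated consequence of an error is removal rather than correction.

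**Conclusion.** The concern holds as a risk of outcome-dependent exclusion that the plan's wording permits. It does not show that bias will occur, and the direction is not fixed for any one subject. Under a targeted-only outcome with the check run by modality, even-handed removal of 5% to 20% of single-modality misses raises the false-pass rate from 6.4% to between 8.1% and 16.1%. That rests on a true ratio of 0.76, sensitivities of 0.684 and 0.90, 72 csPCa subjects, independence and an assumed removal rate. On the pooled reading the pass/fail ratio is safe and only the two reported sensitivities are inflated. Under the systematic-plus-targeted endpoint the flagged csPCa subject is not a miss, and removing him lowers a ratio below 1 slightly. That the effect depends on an unstated modality and an unsettled endpoint is a further reason to rewrite the sentence.

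**What to change.** Delete the example from 5.8.6 and state instead:

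- Logic checks and the CRF, pathology and image comparisons are applied identically to all subjects and both modalities, and are not triggered by whether targeted or systematic cores are positive.
- Each core's origin (micro-ultrasound target, systematic, mpMRI target) and its PRI-MUS score are fixed on the CRF at the end of the procedure, before pathology is available.
- Errors found are corrected to source and logged; 5.9.10 and 5.9.11 should be aligned with this.
- Subjects with negative targeted and positive systematic cores stay in the analysis.

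Pathology need not be hidden from the checks. That would be unworkable, since 5.8.5.1, 5.8.6 and 5.10.2 all rely on comparing it with other records. The cost is a wording change, one CRF line and a query log, with no additional patients.

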### **5.8.7 Identity of study subjects**

At all times throughout the clinical investigation confidentiality shall be observed by all parties involved. All data shall be secured against unauthorized access. Privacy and confidentiality of

information about each subject shall be preserved in the reports and any publication of the clinical investigation data.

It is the responsibility of the Study Coordinator to maintain the privacy of the subject in the throughout the investigation. The Study Coordinator will make a subject's personal information available to the Study Monitor appointed by Exact Imaging, should it be required for monitoring, auditing or inspection by Western IRB if applicable.

It is the responsibility of the Study Coordinator (or designate) to de-identify subjects, and provide the resulting subject identifier to those involved with the analysis of the case data. This subject identifier will be recorded on CRFs, on ExactVu, and on pathology records. Lists of subjects' names and identifying information will be maintained separately from case report forms, and will be accessible to the Study Coordinator (or Urology San Antonio designate).

Similar de-identification will be applied to any DICOM imaging files that may exist for a subject and that may be used by to analyze case data.

Centre	De-identification scheme
Urology San Antonio	On CRFs, on the ultrasound system, and on pathology records, subjects will be identified alphanumerically and sequentially, using USA-EV-0001, USA-EV-0002, etc.

